Moreover, we will focus on cognitive control and affective biases therein, because this process is related to RNT. We will measure two major constituents of cognitive control, i.e. working memory processing and motivational biases of cognitive control (with respectively a working-memory update/ignore emotion task and Pavlovian-to-instrumental transfer task) before and after MBCT/waitlist. We will use this behavioural data to assess whether working memory and motivational biases are indeed (i) related to RNT and MDD, (ii) are changed by MBCT and (iii) whether these changes are related to clinical effects of MBCT.

Additionally, we aim to investigate the timing of change by administering weekly self-report questionnaires.

Section 3: Study Methods

Design

Patients will be assigned to intervention (MBCT + TAU) or waitlist (TAU) based on regular clinical assessment procedure and start of treatment groups. The intervention group performs measurements once before (T0), halfway (T1), and once after MBCT (T2), whereas the waitlist performs measurements once before (T0), once during (T1), and once after a waiting period (T2) of at least 7 weeks, but preferably 8-10 weeks. The wait-list group receives MBCT after this waiting period and subsequently performs measurements halfway (T3) and after MBCT (T4).

Sample size – power calculation

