To compare the intervention (MBCT + TAU) with the waitlist-control (TAU only) group on sociodemographic, outcome, and hypothesized mediating and moderating variables, independent-samples t-test or chi-square test will be used. The effect of treatment (MBCT + TAU versus TAU) will be tested in the intention-to-treat sample using latent growth curve models (LGCM; (Duncan & Duncan, 1995)). The intercept (baseline score of dependent variable) and slope (representing change over time) will be modeled as latent variables from data at pre-treatment (T0), mid-treatment (T1) and post-treatment (T2) (see Figure 1). First, unconditional models will be estimated separately in each group (MBCT + TAU versus TAU) to test whether a linear (0, 4 and 8 weeks) or non-linear trend of change over time would fit the data best. Second, group (MBCT + TAU = 1 ; TAU = 2) will be added to the model as predictor of the latent growth factors. The path from Group to Slope reflects differences in the trajectories of change on the outcome measure(s) between groups whereas the path from Group to Intercept reflect baseline differences on outcome measures. To assess the rate of change within each group, within-subject cohens d effect sizes will be calculated by dividing the mean-difference (T2-T0) by the standard deviation (SD) of the difference, with 0.2, 0.5, 0.8 representing small, medium and large effects respectively. To compare the rate of change between groups, a between group effect size for growth modeling analysis (GMA) will be calculated using the following equation:
$$\frac{\beta_{11} \times \text{time}}{\text{Pooled SD raw scores}}$$

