 (Feingold, 2009), in which β_{11} is the difference between the means of the unstandardized slopes of the MBCT + TAU versus TAU group. β_{11} must be multiplied by time (in our case 8) to obtain the difference between the model-estimated means of both groups at the end of the study (adjusted for baseline differences). Third, potential moderators of treatment effect, such as baseline levels of different measures of RNT, will be added as predictor of the latent growth factors. A significant interaction effect between moderator, group and slope would mean a moderated treatment effect. As a sensitivity analysis and as a basis for the analyses regarding mechanisms of change (for which a minimal effective MBCT-dose is a requisite), the LGCM analyses will be repeated in the per protocol sample (minimal effective dose of ≥ 4 sessions (Teasdale et al., 2000)).

[figure not shown]

Figure 1. Structure of the Latent Growth Curve Models (LGCM) for the different outcome measures that were assessed before (T0), mid-way (T1) and after (T2) treatment. First unconditional models will be run (blue part). Subsequently a conditional model will be run, with group (MBCT + TAU versus TAU) as predictor of the latent growth factors (yellow).

Mediation analyses

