To test for mediation of the effect of MBCT + TAU versus TAU on depressive symptoms (primary outcome; IDS-SR) and overall functioning (secondary outcome; OQ-45) by primary (the different RNT measures (RRS brooding subscale, PTQ, negative intrusive thoughts on BFT) and secondary mediators of interest (FFMQ, SCS)), cross-lagged structural equation models (CLSEM) will be run (Figure 2) in the per protocol sample. For the primary analysis we deliberately choose for a CLSEM approach instead of using the frequently used Process Macro by Hayes (Hayes et al., 2017) (on which power calculation was based) because of practical and content-related reasons. We choose for CLSEM because (i) the nature of the data. We anticipate to have relatively more missing data at specific time points (i.e. the first, second or third measurement moment) because of the COVID-19 pandemic. CLSEM can handle missing data whereas with PROESS all participants with at least one score missing at one of the time points will be deleted from analyses. (ii) CLSEM provides more information on how variables change (each other) over time, i.e. we model (iia) autoregressive and (iib) cross-lagged effects. And (iii) CLSEM enables modeling of individual participants, and because of that, within-person processes can be separated from stable between-person differences by means of inclusion of random intercepts.

Thus, separate three-wave CLSEM will be run to test mediation of the effect of group by potential mediators on outcome measures (IDS-SR and OQ-45). We will include the following paths within those models: autoregression effects (stability effects) for mediators and outcome variables,

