within time correlations between mediator and outcome variables, longitudinal cross-lagged effects of mediator and outcome variables, effect of outcome at T0 on outcome at T2 and mediator at T0 on mediator at T2. In addition, we will test whether group (MBCT + TAU versus TAU) will have a significant differential effect on outcome at T2 (path a), on mediator at T1 (path b), and whether mediating variables at mid-treatment (T1) predict outcome post-treatment (T2). Finally, as a formal test of mediation, the indirect effect of group (MBCT + TAU versus TAU) on outcome at post-treatment (T2) via mediating variables at mid-treatment (T1) will be estimated using bootstrapping procedures (Selig & Preacher, 2009) consisting of 5000 bootstrap samples. We will calculate 95% confidence intervals (CI) of indirect effects (Preacher and Hayes, 2008). To separate within-person processes from stable between-person differences we will repeat the CLSEM models with the inclusion of random intercepts (Hamaker et al., 2015; Mulder & Hamaker, 2021), and compare results.

[figure not shown]

Figure 2. Structure of Cross-Lagged Structural Equation Models (CLSEM) of mediation for outcome at post-treatment (T2) by mediator at mid-treatment (T1). a represents the direct path of group on outcome, b the effect of group on mediator at mid-treatment, c the effect mediator of mid-treatment on outcome at post-treatment, while $b \times c$ represents the indirect path from group on outcome at post-treatment via mediator at mid-treatment. Note. Group = Mindfulness-based Cognitive Therapy (MBCT) + Treatment as usual (TAU) versus TAU, T0 = pre-treatment, T1 = mid-treatment, T2 = post-treatment.

As a sensitivity analysis we will perform a simple mediation analysis by using the PROCESS macro provided by Hayes et al. (2013). Group (MBCT + TAU versus TAU) will be entered as IV, pre- to post-treatment residualized change in depressive symptoms (IDS-SR) as DV, while pre- to mid-treatment residualized change in RNT/rumination (PTQ/RRS brooding subscale) will be entered as mediator. Other potential mediators of interest will be tested in an analogues manner.

Secondary outcomes: experimental tasks

1. Pavlovian to Instrumental Transfer Task

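### The arms are not randomised, yet the treatment-effect and mediation models plan no baseline adjustment beyond the T0 mediator and outcome

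*SAP*

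**What the plan says.** **Allocation** (SAP, the Design part of Section 3): "Patients will be assigned to intervention (MBCT + TAU) or waitlist (TAU) based on regular clinical assessment procedure and start of treatment groups". No randomisation is described.

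**Treatment effect** (SAP, Clinical effects of MBCT: replication and assessment of moderation). For the baseline comparison of the arms, "independent-samples t-test or chi-square test will be used"; nothing says what follows if a difference is found. In the second LGCM step, group "will be added to the model as predictor of the latent growth factors", and no other predictor is listed. The third step brings in "potential moderators of treatment effect, such as baseline levels of different measures of RNT". The between-group effect size is described as the difference between the model-estimated means "of both groups at the end of the study (adjusted for baseline differences").

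**Mediation** (SAP, Mediation analyses). The CLSEM contains autoregressive and cross-lagged paths, the "effect of outcome at T0 on outcome at T2 and mediator at T0 on mediator at T2", and paths from group. The PROCESS sensitivity analysis uses change in mediator and outcome, each residualised on its own T0 score. Neither names a further baseline variable.

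**Elsewhere.** Current versus remitted status and medication status appear as factors in Statistical analyses PIT. Age and gender appear in the control analyses for the PIT and WMUIET tasks. None of them enters the LGCM, CLSEM or PROCESS models.

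**The concern.** The Objectives speak of the beneficial effects of MBCT and of a reduction in symptoms that MBCT induces. Those are causal readings. When arms are formed by clinical assessment and by when a treatment group starts, such readings need either adjustment for baseline variables related to both allocation and change, or wording that does not claim causation.

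The SAP sets out these models path by path, so the absence of covariates is a choice made in this document and not a detail left to the protocol. Confidence intervals from the planned models reflect sampling error only and would not show this source of error. Because the formal mediation test is the product b×c, confounding of path b passes into the primary mediation result.

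**Working it through.** **1. The plan's own figure.** Inputs (SAP, Sample size – power calculation): group–outcome r = .18, group–mediator r = .27, mediator–outcome r = .26, 95% confidence level. Simulating the simple mediation model (4,000 replications, 4,000 draws) gives power of 80.7% at n = 174 and 78.5% at n = 170. So 174 reproduces if 80% power was the target, which the SAP does not state. The point below does not depend on this figure. The source trial is titled as randomised in the References, so these correlations carry no allowance for non-random allocation.

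**2. What each model conditions on at baseline.**
- LGCM, step 2: group only. Group-to-intercept captures the arm difference in the outcome's own baseline level.
- CLSEM: T0 mediator and T0 outcome.
- PROCESS: the T0 score of each variable, through residualisation.

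**3. When group-to-slope is biased.** Let a characteristic U differ in mean by δ between arms.
- If U adds the same amount γ at every wave, the arm difference in intercept changes by γδ and the slope difference by 0. Group-to-slope is not biased.
- If U also changes the slope by λ per week, group-to-slope is biased by λδ. The numerator of the planned effect size, which multiplies the slope difference by 8, is biased by 8λδ.

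So the exposure in the LGCM is limited to characteristics that differ by arm *and* predict change. This exemption belongs to the slope and does not carry over automatically to models that condition on T0 scores.

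**4. Illustration on the residual-change scale.** This is the scale of the sample-size inputs and of PROCESS; it does not transfer to the LGCM slope.
- With equal arms (assumed), d = 2r/√(1 − r²). For r = .18, d = .36/.984 = 0.37. For r = .27, d = .54/.963 = 0.56.
- Bias in SD of residual change = (standardised arm difference in U) × (association of U with residual change).

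| Assumed arm difference | Assumed association | Bias (SD) | Share of 0.37 | Share of 0.56 |
|---|---|---|---|---|
| 0.2 | 0.1 | 0.02 | 5% | 4% |
| 0.3 | 0.2 | 0.06 | 16% | 11% |
| 0.5 | 0.4 | 0.20 | 55% | 36% |

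With path c held fixed, b×c moves by the same share as b. If the two links of U push in the direction of benefit, the effect is inflated; if against it, a real effect is hidden. If U does not differ by arm, the bias is zero.

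**5. Does conditioning on T0 remove it?** A simulation at n = 174 had no true group effect, an arm difference of 0.5 SD, an association of 0.3 with residual change and an assumed link of 0.3 between U and the T0 outcome. The mean estimated group effect was 0.14 SD when adjusting for T0 outcome only, against 0.5 × 0.3 = 0.15 by the formula. It was 0.003 SD once U was added. Under these assumptions the T0 score absorbs little, and measuring and including U removes the bias.

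**The case against.** **The SAP does not show that the arms differ.** This is true, and it bears on size. It does not supply a plan for the case that they do.

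**Several provisions already deal with baseline differences.** Each falls short of covering the group paths.
- T0 IDS-SR will carry part of current-versus-remitted status, but need not carry medication status or other predictors of change.
- The third LGCM step conditions that model on baseline RNT and perhaps other moderators. It does not adjust the step-2 treatment effect.
- The random-intercept repeat of the CLSEM separates stable differences in mediator and outcome. It does not remove characteristics that differ by arm and affect change.
- The parenthesis about baseline differences in the effect-size text refers to the outcome's own baseline level. It makes no claim of covariate adjustment, so it is not an error.

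**Full adjustment would overload the CLSEM.** This stands. The SAP lists about 12 regression paths (4 autoregressive, 4 cross-lagged, 2 from T0 to T2, 2 from group). Four covariates on four variables would add 16. With five mediators ("RRS brooding subscale, PTQ, negative intrusive thoughts on BFT) and secondary mediators of interest (FFMQ, SCS") and two outcomes there are ten models, at about 200 × 0.85 = 170 patients, or fewer per protocol. The fix therefore uses one score.

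**Stronger readings to avoid.** A reader might infer that a modest hidden imbalance would overturn the primary mediation result. The documents do not support that: they contain no information on imbalance, and the group path in b×c is planned at r = .27, not at the weaker total effect of .18. No significance threshold should be quoted. A reader might also infer that the pandemic makes the arms differ by period. The SAP mentions it only as a reason for missing data at particular time points, "i.e. the first, second or third measurement moment) because of the COVID-19 pandemic". Finally, confounding of path c (mediator to outcome) would exist in a randomised trial too and is not part of this point.

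**Conclusion.** The point holds as an exposure to bias, not as a demonstrated bias. Under the models as written, group-to-slope, path a, path b and therefore b×c are open to confounding by baseline characteristics that differ by arm and predict change, and nothing in the plan removes that.

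The size cannot be derived from the SAP. The 0.02 to 0.20 SD range rests on assumed imbalances and associations, equal arms and a single omitted characteristic. It applies to residual change only, and the true value may be zero.

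This is a cheap improvement: the candidate covariates are already named in the SAP, but adjustment will not turn the comparison into a randomised one.

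**What to change.** - Prespecify, independently of the baseline significance tests, a small covariate set from variables that the SAP already names. Current versus remitted status, medication status, age and gender are an example. The condition is that they are recorded for all MDD patients; the SAP names them only for the task analyses.
- LGCM: add them as predictors of intercept and slope.
- PROCESS: add them as covariates.
- CLSEM: enter them through one prespecified propensity score, predicting mediator and outcome at T1 and T2, as an adjusted analysis.
- Report adjusted and unadjusted results side by side, and describe them as a non-randomised comparison, because unmeasured confounding remains.
- Consider recruitment period only if the arms overlap in calendar time. Group start partly determines allocation, so overlap may be poor.

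**Cost.** No new data if the condition above is met. With four covariates, each entered as a single term, the LGCM gains 4 × 2 = 8 paths per outcome. Each CLSEM gains about 4. A rule for missing covariate values is needed.

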Before start of the study, a sample size calculation for the primary analysis (mediation analysis) was conducted using the Monte Carlo Power Analysis Application provided by Schoemann, Boulton, & Short (2017) (https://schoemann.shinyapps.io/mc_power_med/). This tool enables the researcher to calculate a required sample size for (simple) mediation models by using correlations between the independent variable (IV), dependent variable (DV), and mediator (M). We based the required sample size for the mediation analysis on previously published data on the effectiveness of MBCT for chronic, treatment-resistant depressed patients (Cladder-Micus et al., 2018). We based the calculation on 1000 replications, 20000 Monte Carlo Draws per replication, and a Confidence Level of 95%. The correlation between IV (condition; MBCT + TAU versus TAU) and DV (residual change in depressive symptom; $r = .18$), IV and mediator (residual change in RRS brooding score; $r = .27$), and mediator and DV ($r = .26$) were entered in the application. Based on this calculation, 174 participants would be required. Based on previous studies reporting a drop-out between 10% (Van Aalderen et al., 2012) and 24.5% (Cladder-Micus et al., 2018), we therefore expected a drop-out of 15% and aimed to include 200 participants.

Statistical analysis

Clinical effects of MBCT: replication and assessment of moderation

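### The recruitment aim of 200 leaves 170 participants after the stated 15% drop-out, not the required 174; retaining 174 needs 205

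*SAP*

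**What the plan says.** The SAP section on sample size and power bases the calculation on a simple mediation model, with three correlations taken from an earlier MBCT trial in chronic, treatment-resistant depression: .18 between condition and outcome, .27 between condition and mediator, and .26 between mediator and outcome. It reports the result as "Based on this calculation, 174 participants would be required".

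The next sentence cites drop-out of 10% and 24.5% in two earlier studies and concludes: "we therefore expected a drop-out of 15% and aimed to include 200 participants".

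The section gives no inflation formula. It does not say that 200 is rounded, or that ending with fewer than 174 is acceptable. No other section of the SAP returns to the figure.

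**The concern.** The aim of 200 is presented as the consequence of needing 174 and expecting to lose 15%. Drop-out is ordinarily a share of the people enrolled, so the required number should be divided by the share retained. Adding 15% of the required number to itself gives too small an allowance, and 200 looks like the result of doing that.

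If so, the trial would plan from the start to end below its own calculated requirement, and a reader checking the paragraph could not get from its inputs to its conclusion. What is at stake is whether the sample size statement can be reproduced and, to a small degree, the power of the mediation analysis.

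**Working it through.** **Inputs, all from the SAP's sample size section**

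- Required number: 174
- Expected drop-out: 15%
- Recruitment aim: 200
- Drop-out in the cited studies: 10% and 24.5%
- Correlations: .18, .27 and .26
- Calculation settings: 1000 replications, 20000 draws per replication, 95% confidence level

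**Step 1. Reproducing the stated 200**

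- Required number × (1 + drop-out) = 174 × 1.15 = 200.1, which matches 200.
- This agreement suggests a cause but does not prove one, because the SAP does not show how it reached 200.

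**Step 2. What 200 leaves**

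- Aim × (1 − drop-out) = 200 × 0.85 = 170.
- Shortfall against the requirement: 174 − 170 = 4.
- Largest drop-out at which 200 still retains 174: 1 − 174/200 = 13%.

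**Step 3. What 174 needs**

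- Required number / (1 − drop-out) = 174 / 0.85 = 204.7, rounded up to 205.
- Check: 204 × 0.85 = 173.4, too few; 205 × 0.85 = 174.25, enough.
- Gap in the aim: 205 − 200 = 5, and 5/205 = 2.4%.

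**Step 4. The same sums across the cited drop-out range**

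| Drop-out | Left from 200 | Enrolment that retains 174 |
|---|---|---|
| 10% | 180 | 194 |
| 13% | 174 | 200 |
| 15% | 170 | 205 |
| 24.5% | 151 | 231 |

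**Step 5. Effect on power**

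The simple mediation model was re-simulated with the SAP's correlations, a 95% Monte Carlo interval for the indirect effect, 20000 draws, and two runs of 60,000 replications at each sample size.

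- N = 174: .7986 and .7962, pooled .797.
- N = 170: .7824 and .7867, pooled .785.
- Difference: about 1.3 points, with a standard error of about 0.17 points.

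A separate, smaller simulation (6000 replications, 2000 draws) gave .793 at 174, .782 at 170 and .724 at 151, in line with these results.

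For scale, the Monte Carlo standard error of a power estimate near 80% from 1000 replications is √(.8 × .2 / 1000) = .013, or 1.3 points.

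The SAP states no power target. Its 174 is consistent with a target of 80%, but that is an inference, and the power figures here are re-simulation results, not SAP figures.

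**The case against.** The strongest case on the other side accepts the arithmetic and argues that it does not matter.

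- **Noise in 174.** Over this range, 4 participants are worth about one Monte Carlo standard error of the calculation that produced 174. A rerun with the same settings could return a number a few participants higher or lower, so 174 is not a hard floor.
- **The 15% is a judgement.** It was chosen from within a range of 10% to 24.5%. Across that range an aim of 200 leaves anything from 180 down to 151, a spread of 29 that dwarfs a gap of 4. At any drop-out up to 13%, the aim is sufficient.
- **A round aim.** 200 can be read as a convenient recruitment figure and not as an exact derivation.
- **Missing data.** The Mediation analyses section chooses cross-lagged structural equation models partly because they can use incomplete records, so not every drop-out need be lost to the primary analysis.

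The first two points stand as limits on the importance of the error. The third is possible, but the SAP does not say so, and rounding 205 down to 200 misses the stated requirement. The fourth is fair but only partial. The 174 was calculated for the simple mediation approach, in which, by the SAP's own account, anyone with a missing score is deleted, and that approach is kept as a sensitivity analysis. The cross-lagged models are also restricted to the per protocol sample (at least 4 sessions). None of these points makes 174, 15% and 200 consistent with one another.

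**Conclusion.** The concern holds, as a minor arithmetic error. On the SAP's own inputs the aim is 5 too low (200 against 205, or 2.4%), and it leaves 4 fewer than required (170 against 174). This rests only on reading drop-out as a share of those enrolled and on the SAP's three stated numbers.

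The cost in power is about 1.3 points for the simple mediation model, from about 80% to 78–79%. That estimate takes the SAP's correlations as given and treats every drop-out as lost to the analysis. It does not show a materially underpowered trial, and no analysis or decision in the SAP depends on it.

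**What to change.** Amend the last sentence of the sample size section in one of two ways.

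1. Keep 200 and add that an aim of 200 leaves about 170 participants after 15% drop-out, 4 fewer than the calculated 174. This is the better choice, because the paragraph records what was decided before the study began and the historical aim should stay visible.
2. State that 205 is the number that would retain 174 at 15% drop-out. If this is used, it should stand beside the original aim of 200 and not overwrite it.

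A power figure is not needed. If one is added, it should be labelled as a re-simulation of the simple mediation model.

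The cost is one sentence or one number. Enrolment and analysis stay as they are.

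### The only sensitivity analysis of the intention-to-treat growth model removes early stoppers, so no planned check tests what the model assumes about MBCT patients who stop and have no later scores

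*SAP*

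**What the plan says.** In the SAP section on the clinical effects of MBCT, "The effect of treatment (MBCT + TAU versus TAU) will be tested in the intention-to-treat sample using latent growth curve models". The intercept and slope "will be modeled as latent variables from data at pre-treatment (T0), mid-treatment (T1) and post-treatment (T2". Group is then added as a predictor of both, and the path from group to slope carries the treatment effect. Sessions attended do not enter this model. The one sensitivity analysis named for it is that "the LGCM analyses will be repeated in the per protocol sample (minimal effective dose of ≥ 4 sessions". The same sentence gives that run a second purpose, as the basis for the analyses of mechanisms.

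Other parts of the SAP bear on the point:

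- Design: "The intervention group performs measurements once before (T0), halfway (T1), and once after MBCT (T2". The section neither ties measurement to attendance nor says whether patients who stop MBCT are still measured. On allocation it says: "Patients will be assigned to intervention (MBCT + TAU) or waitlist (TAU) based on regular clinical assessment procedure and start of treatment groups".
- Sample size: after citing drop-out of 10% and 24.5% in earlier studies, "we therefore expected a drop-out of 15% and aimed to include 200 participants".
- Mediation analyses: "cross-lagged structural equation models (CLSEM) will be run (Figure 2) in the per protocol sample". The SAP's only statement on missing-data handling is here: "CLSEM can handle missing data whereas with PROESS all participants with at least one score missing at one of the time points will be deleted". There is no counterpart for the LGCM.

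**The concern.** An MBCT patient who stops early and has only a T0 score carries no information on change. If the LGCM is fitted by likelihood to all available scores, that patient is in effect assigned the slope estimated from MBCT patients who were measured later. If such patients are deleted instead, the slope again rests on those who were measured.

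That assumption sits badly with the SAP's own premise. By treating 4 sessions as the least that is effective, the SAP implies that patients who stop sooner should gain less. Yet the only planned check on the model restricts it to patients at or above that threshold. This takes out the patients in question and moves further towards attenders. If the two results agree, a reader will take it as robustness, although for this group both rest on much the same patients.

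Objective (i) is to replicate the effect of MBCT on depressive symptoms and repetitive negative thinking. At stake is how far the result labelled intention-to-treat can be trusted to include patients who did not stay.

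**Working it through.** **The plan's own figure.** The SAP gives no power or effect figure for the LGCM. Its sample size is for mediation. With its correlations (.18, .27, .26) and a 95% Monte Carlo interval, simulated power at 174 participants is 0.807, so 174 reproduces if 80% power was the target (the SAP does not state it). For 15% drop-out, 174 × 1.15 = 200.1 and 174 / 0.85 = 204.7, so the stated 200 is close either way.

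**Inputs from the SAP.** Correlation of group with residual symptom change, r = .18; drop-out of 10%, 15% and 24.5%; waves at 0, 4 and 8 weeks.

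**Assumptions not in the SAP.** Groups of equal size; full-information maximum likelihood; all drop-out in the MBCT arm and due to stopping MBCT; stoppers follow the TAU slope; outcome SD 12; intercept variance 100, slope variance 0.6, residual variance 44.

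**Step 1, effect in those who stay.** d = 2r / √(1 − r²) = 0.36 / √(1 − 0.0324) = 0.366.

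**Step 2, effect with stopping counted.** If a proportion p stop and gain nothing over TAU, it is d(1 − p): 0.329 at 10%, 0.311 at 15%, 0.276 at 24.5%. A model that returns 0.366 overstates this by 1/(1 − p) − 1, which is 11%, 18% and 32%. In SD units the gaps are 0.037, 0.055 and 0.090.

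**Step 3, what the growth model returns.** The 0/4/8-week LGCM was simulated with 60,000 patients. Values are effect sizes in SD units. True means the simulated T2 difference with stopping counted, except in the last two rows, where it is d(1 − p).

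| Stoppers | p | True | ITT model | Per protocol | ITT / true |
|---|---|---|---|---|---|
| Leave before T1 | 10% | 0.328 | 0.365 | 0.365 | 1.11 |
| | 15% | 0.315 | 0.371 | 0.371 | 1.18 |
| | 24.5% | 0.277 | 0.365 | 0.365 | 1.32 |
| Leave after T1, TAU slope throughout | 10% | 0.334 | 0.357 | 0.368 | 1.07 |
| | 15% | 0.301 | 0.342 | 0.362 | 1.14 |
| | 24.5% | 0.258 | 0.318 | 0.350 | 1.23 |
| Leave after T1, TAU slope from then on | 10% | 0.350 | 0.371 | 0.369 | 1.06 |
| | 15% | 0.327 | 0.354 | 0.353 | 1.08 |
| | 24.5% | 0.319 | 0.364 | 0.367 | 1.14 |
| Stop but still measured | 15% | 0.311 | 0.309 | 0.364 | 0.99 |
| | 24.5% | 0.276 | 0.273 | 0.362 | 0.99 |

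The simulated values carry error of about 0.01 (compare 0.301 with the formula's 0.311), so the ratios are approximate. At 15% with T1 available the overstatement is 8% to 14% from three-decimal values, or 6% to 13% if the values are first rounded to two decimals. The per-protocol column excludes every stopper. Under the SAP's rule, a patient who stops after 4 or more sessions stays in.

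**Reading.** When stoppers have only T0, the intention-to-treat and per-protocol estimates coincide and both miss the true effect. When stoppers are still measured, the intention-to-treat model gives the right answer and differs visibly from per protocol.

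**The case against.** A reader might infer that no planned analysis counts stopping at all, or that the intention-to-treat result is a per-protocol result under another name. The document does not support that. T1 and T2 are scheduled for the whole intervention group, without any condition on attendance. A patient who stops sessions but completes the questionnaires is counted correctly, and comparing the two samples is then informative. Whether stoppers are followed up may be settled in the protocol, which is not at hand. This objection stands, and it limits the point to stoppers without later scores.

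Four further objections carry weight:

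- The SAP names no estimator for the LGCM, so the slope given to unmeasured stoppers is inferred from usual practice. A stopper with a T1 score contributes it, so the substitution is then only partial.
- The 10%, 15% and 24.5% are overall drop-out figures. The SAP does not say that they are MBCT discontinuations, that they fall in one arm, or that T1 and T2 are then missing. It links the extra missing data it expects to COVID-19.
- Even under the worst-case assumptions, the gap at 15% is 0.055 SD. With 174 patients in equal groups, the standard error of d is roughly 2/√174 = 0.15.
- Allocation is not randomised, so the effect of assignment is not cleanly identified even with complete data, and imputing from the waitlist inherits any confounding.

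These objections lower the size and certainty of the bias. They do not supply the missing check. The random-intercept and PROCESS repeats concern mediation, and nothing planned for the LGCM keeps all intention-to-treat patients while varying the assumption about those who left.

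**Conclusion.** The point holds in a limited form. For MBCT patients who stop and have no later scores, the intention-to-treat LGCM rests on an unstated assumption, and the only sensitivity analysis named for it cannot test that assumption. Agreement between the two runs would therefore not show robustness on this point.

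The overstatement lies between zero (stoppers gain as much as the rest, or are still measured) and about 11%, 18% and 32% at 10%, 15% and 24.5% drop-out. The upper figures need all drop-out to be MBCT stopping, in the MBCT arm only, without later scores and without benefit. With T1 available, the overstatement is roughly 6% to 23% across the three rates. These are illustrations, not estimates of the bias in this trial. The matter is an inexpensive improvement and gives no ground for replacing the main analysis.

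**What to change.** Keep the LGCM in the intention-to-treat sample as the main analysis and make these changes to the SAP:

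1. State the estimator and the missing-data assumption of the LGCM.
2. Add one pre-specified sensitivity analysis in the full intention-to-treat sample. Multiply impute the missing T1 and T2 scores of MBCT patients who stopped from the waitlist (TAU) trajectory. Impute other missing scores, such as those due to COVID-19, within arm, with sessions attended in the imputation model. Refit the LGCM and report the group-to-slope path and the Feingold effect size.
3. Where the reason for a missing score is not recorded, define stopping for this analysis as fewer than 4 sessions attended, the SAP's own threshold.
4. Describe the per-protocol LGCM as an effect in attenders and as groundwork for the mechanism analyses, not as a check on the intention-to-treat result.

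The cost is some SAP wording and one imputation run. The split in step 2 works best if reasons for missing visits are recorded, which the SAP does not confirm. The added estimate will usually be less favourable to MBCT. It addresses bias from missing data only and leaves confounding from non-random allocation untouched.
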